8.1 Site monitoring

Before study initiation, at a site initiation visit or at an investigator's meeting, a Novartis representative will review the protocol and CRFs with the investigators and their staff. During the study, the field monitor will visit the site regularly to check the completeness of subject records, the accuracy of entries on the CRFs, the adherence to the protocol and to Good Clinical Practice, the progress of enrollment, and to ensure that study treatment is being stored, dispensed, and accounted for according to specifications. Key study personnel must be available to assist the field monitor during these visits.

The investigator must maintain source documents for each subject in the study, consisting of case and visit notes (hospital or clinic medical records) containing demographic and medical information, laboratory data, electrocardiograms, and the results of any other tests or assessments. All information on CRFs must be traceable to these source documents in the subject's file. The investigator must also keep the original informed consent form signed by the subject (a signed copy is given to the subject).

The investigator must give the monitor access to all relevant source documents to confirm their consistency with the CRF entries. Novartis monitoring standards require full verification for the presence of informed consent, adherence to the inclusion/exclusion criteria, documentation of SAEs, and of data that will be used for all primary variables. Additional checks of the consistency of the source data with the CRFs are performed according to the study-specific monitoring plan. No information in source documents about the identity of the subjects will be disclosed.

8.2 Data collection

Designated investigator staff will enter the data required by the protocol into the OC/RDC system. Designated investigator site staff will not be given access to the system until they have been trained.

Automatic validation procedures within the system check for data discrepancies during and after data entry and, by generating appropriate error messages, allow the data to be confirmed or corrected online by the designated investigator site staff. The Investigator must certify that

the data entered into the electronic Case Report Forms are complete and accurate. After DBL, the investigator will receive copies of the subject data for archiving at the investigational site.

8.3 Database management and quality control

Novartis staff review the data entered into the CRFs by investigational staff for completeness and accuracy and instruct the site personnel to make any required corrections or additions. Queries are sent to the investigational site using an electronic data query. Designated investigator site staff is required to respond to the query and confirm or correct the data. If the electronic query system is not used, a paper Data Query Form will be faxed to the site. Site personnel will complete and sign the faxed copy and fax it back to Novartis staff that will make the correction to the database. The signed copy of the Data Query Form is kept at the investigator site.

Concomitant medications entered into the database will be coded using the WHO Drug Reference List, which employs the Anatomical Therapeutic Chemical classification system. Concomitant procedures, non-drug therapies and adverse events will be coded using the Medical dictionary for regulatory activities (MedDRA) terminology.

Laboratory samples will be processed centrally and the results will be sent electronically to Novartis (or a designated CRO). Novartis Data Management staff will perform a reconciliation of the data entered into the eCRF versus what is received from the central laboratory. At a minimum this reconciliation will include header reconciliation, visit window checks, duplicate record checks, out of range checks as defined by the Clinical Trial Team and checks to address missing laboratory data.

ECG readings will be processed centrally and the results will be sent electronically to Novartis (or a designated CRO).

Data about all study drug(s) dispensed to the subject and all dosage changes will be tracked using an Interactive Response Technology (IRT). The system will be supplied by a vendor, who will also manage the database. The database will be sent electronically to Novartis (or a designated CRO).

8.4 Data Monitoring Committee

An independent data monitoring committee (DMC) reviewed the safety data of this trial at regular intervals. Details regarding the DMC process are available in relevant secukinumab DMC charters. Following the Week 52 DBL and interim analysis, the DMC review will no longer be required.

8.5 Adjudication Committee

An independent adjudication committee will be used to monitor specific safety events, including but potentially not limited to clinically significant cardio- and cerebro-vascular events. The events will be blindly reviewed and adjudicated as they occur during the conduct of the trial.

Details regarding the adjudication process will be available in relevant secukinumab Adjudication Committee charters.

9 Data analysis

Summary statistics for continuous variables will generally include the number of subjects (N), minimum, lower quartile, mean, median, upper quartile, and maximum. For categorical or binary variables, the number and percent of subject in each category will be presented. The 95% confidence intervals will be provided to evaluate the treatment efficacy.

Data will be presented by a combination of the ‘original’ and ‘switch’ treatment groups. These treatment groups represent the treatment combinations the subjects experience over the course of the entire trial in case of re-randomization and dose escalation.

Note that the treatment groups for a subject may differ depending on the time period of the analysis and whether one assesses the subject for efficacy or safety.

9.1 Analysis sets

The following analysis sets will be used in this study:

Full analysis set (FAS): The FAS will be comprised of all subjects enrolled in the study.

Safety set: The safety set includes all subjects enrolled in the study who took at least 1 dose of study treatment during the study.

9.2 Subject demographics and other baseline characteristics

Summary statistics will be presented for continuous demographic and baseline characteristic variables for each treatment group and for all subjects enrolled in the study. The number and percentage of subjects in each category will be presented for categorical variables for each treatment group and all subjects.

9.3 Treatments

9.3.1 Study Treatment

The analysis of study treatment data will be based on the safety set. The duration of exposure to study treatment will also be summarized by treatment group. In addition, the number and percentage of subjects with cumulative exposure levels will be presented.

9.3.2 Concomitant medication

Concomitant medications will be summarized by treatment group. Any medication given at least once between the start of the first dose in this extension trial and the date of the last study visit in the extension study will be a concomitant medication, including those which were started before Week 104E1 and continued into the extension study where study treatment is administered.

Medications will be presented in alphabetical order, by Anatomical Therapeutic Classification (ATC) codes and grouped by anatomical main group. Tables will show the overall number and percentage of subjects receiving at least one treatment of a particular ATC code and at least one treatment in a particular anatomical main group.

Significant medical surgeries and procedures will be summarized by primary system organ class and MedDRA preferred term.

The number and percentage of subjects receiving concomitant rheumatoid arthritis therapy will be presented by treatment group as well as the reasons for stopping their therapies (primary lack of efficacy, secondary lack of efficacy, lack of tolerability, other) and the total duration of exposure to rheumatoid arthritis therapies previously.

9.4 Analysis of the primary and key secondary variable(s)

9.4.1 Variable(s)

The primary efficacy variable is the clinical response to treatment according to the ASAS20 over time up to Week 260. The analysis of the primary variable will be based on the FAS subjects.

9.4.2 Statistical model, hypothesis, and method of analysis

No formal hypotheses are proposed for this study. The proportion of subjects meeting the ASAS20 will be descriptively summarized for each treatment over time. Treatment efficacy will be assessed by providing the 95% confidence interval of treatment response according to the ASAS criteria. No statistical comparison is expected to be performed between treatment groups.

9.4.3 Handling of missing values/censoring/discontinuations

Efficacy data will be presented using all available data at the given time point of analysis.

Additionally, under the assumption of missing at random, multiple imputation by treatment may be performed for baseline weight as well as for all baseline and post-baseline efficacy variables of interest during the trial.

9.4.4 Supportive analyses

Sensitivity analysis may be performed to assess the robustness of missing data handling. These may include multiple imputation for ASAS20.

9.5 Analysis of secondary [REDACTED] variables

9.5.1 Efficacy variables

For binary variables, the proportion of responders will be summarized over analysis visits. For continuous variables, the change from baseline (of core) will be presented. The 95% confidence intervals will be provided to evaluate the long-term treatment efficacy of the secondary binary variables of interest. Summary statistics for continuous variables include mean, standard deviation, minimum, lower quartile, median, upper quartile and maximum.

Secondary variables include:

- The proportion of subjects achieving ASAS40

No statistical comparisons between any of the treatment groups (75 mg treatment arm and 150 mg treatment arm including patients who escalated from 75 mg s.c. to 150 mg s.c. every 4 weeks) will be provided for the analysis of the secondary [REDACTED] variables.

9.5.2 Safety variables

Adverse events

Treatment emergent adverse events (events started after the first dose of study treatment in the extension or events present prior to the first dose of study treatment in core study but increased in severity based on preferred term and within 84 days after last dose of secukinumab) will be summarized.

AEs will be summarized by presenting, for each treatment group, the number and percentage of subjects having any AE, having an AE in each primary system organ class and having each individual AE (preferred term). Summaries will also be presented for AEs by severity and for study treatment related AEs. If a subject reported more than one adverse event with the same preferred term, the adverse event with the greatest severity will be presented. If a subject reported more than one adverse event within the same primary system organ class, the subject will be counted only once with the greatest severity at the system organ class level, where applicable. Serious adverse events will also be summarized.

The incidence of AEs will be presented per 100 subject years of exposure.

Separate summaries will be provided for death, serious adverse event, other significant adverse events leading to discontinuation and adverse events leading to dose adjustment (including study treatment discontinuation).

A graphical display of relative frequencies within system organ classes and relative risks, as appropriate, will be presented.

When adjudication is required of major cardiovascular adverse events, a summary of those types of events as reported by the investigator and confirmed by adjudication will be provided.

Laboratory data

The summary of laboratory evaluations will be presented for three groups of laboratory tests (hematology, serum chemistry and urinalysis). Descriptive summary statistics for the change from baseline to each study visit will be presented. These descriptive summaries will be presented by test group, laboratory test and treatment group. Change from baseline will only be summarized for subjects with both baseline of core study and post baseline values.

For each parameter, the maximum change from baseline within each study period will be evaluated analogously.

[figure not shown]
In addition, shift tables will be provided for all parameters to compare a subject's baseline laboratory evaluation relative to the visit's observed value. For the shift tables, the normal laboratory ranges will be used to evaluate whether a particular laboratory test value was normal, low, or high for each visit value relative to whether or not the baseline value was normal, low, or high. These summaries will be presented by laboratory test and treatment group. Shifts will be presented by visit as well as for most extreme values post-baseline.

Vital signs

Analysis of the vital sign measurements using summary statistics for the change from baseline for each post-baseline visit will be performed. These descriptive summaries will be presented by vital sign and treatment group. Change from baseline will only be summarized for subjects with both baseline and post-baseline values.

ECG

Summary statistics will be presented for ECG variables by visit and treatment group. Qualitative changes will be summarized.

9.6 Interim analyses

Interim analyses may be planned in order to support regulatory filing and for purposes of publication after subjects complete additional years of treatment in this extension study. Additional analyses may be performed to support health authority interactions, as necessary.

9.7 Sample size calculation

It is estimated that approximately 75% to 85% of subjects enrolled in the core study will complete the entire treatment period and be eligible for entry into the extension study, which is equivalent to about 279 to 316 subjects.

10 Ethical considerations

10.1 Regulatory and ethical compliance

This clinical study was designed and shall be implemented and reported in accordance with the ICH Harmonized Tripartite Guidelines for Good Clinical Practice, with applicable local regulations (including European Directive 2001/20/EC, US Code of Federal Regulations Title 21, and Japanese Ministry of Health, Labor, and Welfare), and with the ethical principles laid down in the Declaration of Helsinki.

10.2 Informed consent procedures

Eligible subjects may only be included in the study after providing written (witnessed, where required by law or regulation), IRB/IEC-approved informed consent, or, if incapable of doing so, after such consent has been provided by a legally acceptable representative of the subject. In cases where the subject's representative gives consent, the subject should be informed about the study to the extent possible given his/her understanding. If the subject is capable of doing so, he/she should indicate assent by personally signing and dating the written informed consent document or a separate assent form. Informed consent must be obtained before conducting any study-specific procedures (i.e. all of the procedures described in the protocol). The process of obtaining informed consent should be documented in the subject source documents.

Novartis will provide to investigators in a separate document a proposed informed consent form that complies with the ICH GCP guideline and regulatory requirements and is considered appropriate for this study. Any changes to the proposed consent form suggested by the investigator must be agreed to by Novartis before submission to the IRB/IEC, and a copy of the approved version must be provided to the Novartis monitor after IRB/IEC approval.

Women of child bearing potential should be informed that taking the study treatment may involve unknown risks to the fetus if pregnancy were to occur during the study and agree that in order to participate in the study they must adhere to the contraception requirement for the duration of the study. If there is any question that the subject will not reliably comply, they should not be entered in the study.

10.3 Responsibilities of the investigator and IRB/IEC

The protocol and the proposed informed consent form must be reviewed and approved by a properly constituted Institutional Review Board/Independent Ethics Committee/Research Ethics Board (IRB/IEC) before study start. A signed and dated statement that the protocol and informed consent have been approved by the IRB/IEC must be given to Novartis before study initiation. Prior to study start, the investigator is required to sign a protocol signature page confirming his/her agreement to conduct the study in accordance with these documents and all of the instructions and procedures found in this protocol and to give access to all relevant data and records to Novartis monitors, auditors, Novartis Clinical Quality Assurance representatives, designated agents of Novartis, IRBs/IECs, and regulatory authorities as required. If an inspection of the clinical site is requested by a regulatory authority, the investigator must inform Novartis immediately that this request has been made.

10.4 Publication of study protocol and results

Novartis assures that the key design elements of this protocol will be posted in a publicly accessible database such as clinicaltrials.gov. In addition, upon study completion and finalization of the study report the results of this trial will be either submitted for publication and/or posted in a publicly accessible database of clinical trial results.

11 Protocol adherence

Investigators ascertain they will apply due diligence to avoid protocol deviations. Under no circumstances should the investigator contact Novartis or its agents, if any, monitoring the trial to request approval of a protocol deviation, as requests to approve deviations will not be granted.

This protocol defines the study objectives, the study procedures and the data to be collected on study participants. Under no circumstances should an investigator collect additional data or conduct any additional procedures for any research related purpose involving any investigational drugs.

If the investigator feels a protocol deviation would improve the conduct of the study this must be considered a protocol amendment, and unless such an amendment is agreed upon by Novartis and approved by the IRB/IEC it cannot be implemented. All significant protocol deviations will be recorded and reported in the CSR.

13.1 Appendix 1: Clinically notable laboratory values and vital signs

The following criteria will be used to define expanded limits and notable abnormalities of key laboratory tests.

Clinically notable values will be forwarded to Novartis at the same time that they are sent to investigators.

Table 13-1 Safety Analyses: Expanded Limits and Notable Criteria

Final Harmonization			
		Notable Criteria	
Laboratory Variable		Standard Units	SI Units
LIVER FUNCTION AND RELATED VARIABLES			
SGOT (AST)		>3 x ULN	>3 x ULN
SGPT (ALT)		>3 x ULN	>3 x ULN
Bilirubin		>2 x ULN	>2 x ULN
Alkaline phosphatase		>2.5 x ULN	>2.5 x ULN
RENAL FUNCTION, METABOLIC AND ELECTROLYTE VARIABLES			
Creatinine (serum)		>2 x ULN	>2 x ULN

[figure not shown]
HEMATOLOGY VARIABLES

Hemoglobin: ≥ 20 g/L decrease from baseline

Platelet count: $< 100 \times 10^9 / L$

White blood cell count: $< 0.8 \times LLN$

Neutrophils: $< 0.9 \times LLN$

13.3 Appendix 3: Modified New York criteria

Clinical criteria

- Low back pain and stiffness for more than 3 months that improves with exercise, but is not relieved by rest
- Limitation of motion of the lumbar spine in the sagittal and frontal planes
- Limitation of chest expansion relative to normal values correlated for age and sex

Radiological criterion

- Sacroiliitis grade ≥ 2 bilaterally or grade 3-4 unilaterally

Definite AS if the radiological criterion is associated with at least one clinical criterion

13.4 Appendix 4: Assessment of SpondyloArthritis International Society criteria (ASAS)

The ASAS response measures consist of the following assessment domains ([Sieper 2009](#)):

Main ASAS domains:

1. Patient's global assessment of disease activity measured on a VAS scale
2. Patient's assessment of back pain represented by either total or nocturnal pain scores, both measured on a VAS scale
3. Function represented by BASFI average of 10 questions regarding ability to perform specific tasks as measured by VAS scale
4. Morning stiffness represented by the average of the last 2 questions on the 6-question BASDAI regarding morning stiffness as measured by VAS scales

Additional assessment domains:

5.

6.

13.4.1 Bath Ankylosing Spondylitis Functional Index (BASFI)

The BASFI is a set of 10 questions designed to determine the degree of functional limitation in those subjects with AS. The ten questions were chosen with a major input from subjects with AS. The first 8 questions consider activities related to functional anatomy. The final 2 questions assess the subject's ability to cope with everyday life. A 10cm visual analog scale is used to answer the questions. The mean of the ten scales gives the BASFI score – a value between 0 and 10.

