12.1 Description of efficacy variables

Assessment of Spondyloarthritis International Society criteria (ASAS) response criteria

The ASAS response measures consist of the following assessment domains ([Sieper 2009](#)).

[figure not shown]
Main ASAS domains:

1. Patient's global assessment of disease activity measured on a VAS scale
2. Patient's assessment of back pain, represented by either total or nocturnal pain scores, both measured on a VAS scale. *For ASAS response analyses, the total back pain will be used.*
3. Function represented by BASFI average of 10 questions regarding ability to perform specific tasks as measured by VAS scale

4. Inflammation represented by mean duration and severity of morning stiffness, represented by the average of the last 2 questions on the 6-question BASDAI as measured by VAS scale (at least one question is needed)

Additional assessment domains:

5. [REDACTED]
6. [REDACTED]

ASAS components

Patient's global assessment of disease activity (VAS)

The patient's global assessment of disease activity will be performed using a 100 mm visual analog scale (VAS) ranging from not severe to very severe, after the question "*How active was your disease on average during the last week?*".

Patient's assessment of total inflammatory back pain and nocturnal back pain intensity (VAS)

The patient's assessment of inflammatory back pain will be performed using a 100 mm VAS ranging from no pain to unbearable pain, after the question "*Based on your assessment, please*

indicate what is the amount of back pain at any time that you experienced during the last week?” and “Based on your assessment, please indicate what is the amount of back pain at night that you experienced during the last week? ”.

Bath Ankylosing Spondylitis Functional Index (BASFI)

The BASFI is a set of 10 questions designed to determine the degree of functional limitation in those subjects with AS. The ten questions were chosen with a major input from subjects with AS. The first 8 questions consider activities related to functional anatomy. The final 2 questions assess the subjects’ ability to cope with everyday life. A 100 mm VAS is used to answer the questions. The mean of the ten scales gives the BASFI score – a value between 0 and 10.

In the case that some of the BASFI questions are missing then the average of the non-missing items will be utilized ([Braun 2009](#), [van Tubergen 2001](#))

Bath Ankylosing Spondylitis Disease Activity Index (BASDAI)

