The gold standard for measuring and evaluating disease activity in AS is the BASDAI. The BASDAI consists of a 0 through 10 scale (0 being no problem and 10 being the worst problem), which is used to answer 6 questions pertaining to the 5 major symptoms of AS:

1. Fatigue
2. Spinal pain
3. Joint pain / swelling
4. Areas of localized tenderness (called enthesitis, or inflammation of tendons and ligaments)
5. Morning stiffness duration
6. Morning stiffness severity

To give each symptom equal weighting, the mean (average) of the two scores relating to morning stiffness is taken. The mean of questions 5 and 6 is added to the score from questions 1-4. If one of questions 5 or 6 is missing, then the non-missing one should be added. The resulting 0 to 50 score is divided by 5 to give a final 0 – 10 BASDAI score. Scores of 4 or greater suggest suboptimal control of disease, and subjects with scores of 4 or greater are usually good candidates for either a change in their medical therapy or for enrollment in clinical trials evaluating new drug therapies directed at AS. BASDAI is a quick and simple index taking between 30 secs and 2 mins to complete.

At least 4 questions should be non-missing to calculate the BASDAI score. Otherwise, BASDAI score will be missing ([Haywood 2002](#)). If both Q5 and Q6 are missing or one of Q1 to Q4 is missing the total sum should be divided by 4 instead of 5. If two of Q1 to Q4 are missing and both Q5 and Q6 are not missing the sum should be divided by 3.

Bath Ankylosing Spondylitis Metrology Index (BASMI linear)

The BASMI is a validated instrument that uses the minimum number of clinically appropriate measurements that assess accurately axial status, with the goal to define clinically significant changes in spinal movement. Parameters include:

1. lateral lumbar flexion (cm)
2. tragus-to-wall distance (cm)

3. lumbar flexion (modified Schober) (cm)
4. maximal intermalleolar distance (cm)
5. cervical rotation angle (°)

Additionally, the following assessments should be taken:

6. occiput-to-wall distance
7. chest expansion

The assessments A of the first five components into the scores S using the equations are given in [Table 12-1 \(van der Heijde et al, 2013\)](#). All 5 components should be non-missing to calculate BASMI.

[figure not shown]
Table 12-1 Equations for the conversion of the assessments A into scores S for the five components of the BASMI linear

[figure not shown]
	$S = 0$ if	Between 0 and 10	$S = 10$ if

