13.1 Variable(s)

The primary efficacy variable is the clinical response to treatment according to the ASAS20 over time up to Week 260. The analysis of the primary variable will be based on the FAS subjects.

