14.1 Efficacy variables

Secondary [REDACTED] variables include:

- the proportion of subjects achieving ASAS40

For binary variables, the proportion of responders along with the 95% CI will be presented by groups according to the treatment sequence over analysis visits. For continuous variables, the change from core baseline will be summarized.

Results will be presented for the FAS, as well as subgroups by TNF α status (naive or IR) for the following variables: ASAS40, [REDACTED]

Graphical representation (line plots) regarding the response over time for the following measures will be provided in the observed data: ASAS20/40, [REDACTED]

[REDACTED] will also be graphically illustrated. The above mentioned figures will show the originally randomized AIN457 treatment groups.

Cumulative probability plots will be employed to display the change from baseline to week 208 illustrating the progression of subjects after 4 years [REDACTED]

Additional figures as in line plots, illustrating the up-titration effect of treatment will be created for the following parameters: ASAS20/40, [REDACTED]

ASAS20

The ASAS Response Criteria (ASAS20) is defined as an improvement of $\geq 20\%$ and ≥ 1 unit on a scale of 10 in at least three of the four main domains and no worsening of $\geq 20\%$ and ≥ 1 unit on a scale of 10 in the remaining domain.

The percentage of subjects experiencing ASAS20 response, followed by the respective 95% CI, will be presented by treatment sequence up to week 260 based on the observed data. The respective summaries will also be provided by TNF- α IR status.

Additional analysis will be based on the imputed responses only for the AIN457 150 mg group.

The percentage of subjects (and the 95% CI) experiencing ASAS20 response after up-titration will be presented in separate tables (observed data). Patients who had at least 1 dose of the up-titrated dose will be included.

[figure not shown]
ASAS40

[figure not shown]
The ASAS 40 response is defined as an improvement of $\geq 40\%$ and ≥ 2 units on a scale of 10 in at least three of the four main domains and no worsening at all in the remaining domain.

[figure not shown]
[figure not shown]
The percentage of subjects experiencing ASAS40 response, followed by the respective 95% CI will be presented by treatment sequence up to week 260 based on the observed data. The respective summaries will also be provided by TNF- α IR status.

[figure not shown]

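### SAP 12.1 averages whatever BASFI items are answered, with no minimum, so a score from one or two items can settle ASAS20/40 for a borderline subject

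*Protocol*

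**What the plan says.** - **Protocol 6.4.1.7 and Appendix 4 (13.4.1)** define BASFI on a 0-10 scale: "The mean of the ten scales gives the BASFI score". Neither says what happens when items are unanswered.
- **SAP 12.1** gives the same ten-scale definition, then adds: "In the case that some of the BASFI questions are missing then the average of the non-missing items will be utilized". Two publications are cited for the rule. No minimum number of items is stated there, in SAP 12.3 (missing data) or in SAP 19.2.4 (multiple imputation).
- **SAP 12.1** makes BASFI main ASAS domain 3: "Function represented by BASFI average of 10 questions regarding ability to perform specific tasks as measured by VAS scale".
- **SAP 12.1** states a minimum for the other multi-item scores. For morning stiffness, "at least one question is needed". For the BASDAI total, "At least 4 questions should be non-missing to calculate the BASDAI score". For BASMI, "All 5 components should be non-missing to calculate BASMI".
- **SAP 13.1** sets the primary variable: "The primary efficacy variable is the clinical response to treatment according to the ASAS20 over time up to Week 260". SAP 14.1 requires, for ASAS20, improvement of at least 20% and 1 unit "in at least three of the four main domains and no worsening of" at least 20% and 1 unit in the remaining one. ASAS40 requires 40% and 2 units, and allows no worsening in the remaining domain.
- **SAP 12.3** bases the analysis on observed data. Multiple imputation is limited to the originally randomized 10 mg/kg - 150 mg group, and SAP 19.2.4 describes it for visits up to Week 156.

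**The concern.** The ten BASFI items concern different tasks. Eight relate to functional anatomy and two to coping with everyday life. If a ten-item core baseline is compared with a follow-up score built from one or two items, the change reflects which items were answered as well as any change in function. Under the SAP rule that score counts as observed. It therefore enters the main analysis at face value, and multiple imputation, which fills only missing values, would leave it in place. At stake is the response status of subjects whose ASAS20 or ASAS40 result turns on the function domain.

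**Working it through.** The documents give no figure to reproduce, because the point concerns a scoring rule. Four checks follow.

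**1. When does BASFI decide ASAS20?** Classify each of the other three main domains as improved, neutral or worsened beyond the limit, giving 3 x 3 x 3 = 27 states. BASFI alone settles the response in 4 of them:
- two improved and one neutral (3 states): a response only if BASFI improves;
- all three improved (1 state): a response unless BASFI worsens beyond the limit.

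This counts states and is not a probability.

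**2. Error of a k-item score.** If k of the ten items are answered at random and s is the within-subject SD between items, then

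SD(k-item mean - ten-item mean) = s x sqrt[(1/k)(1 - k/10)].

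The documents give no s, so it is assumed. With s = 2:
- k = 1: 2 x sqrt(0.9) = 1.90 units
- k = 3: 2 x sqrt(0.333 x 0.7) = 0.97 units
- k = 7: 2 x sqrt(0.143 x 0.3) = 0.41 units

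The ASAS20 absolute limit is 1 unit.

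**3. Chance of false domain improvement.** Simulation of 400,000 subjects per setting, with these assumptions: subject means around 5.5 (SD 2, kept within 0-10), ten items at baseline, k random items at follow-up, and no true change. The count is of falls of at least 1 unit and at least 20%.

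| Items answered | s = 1.0 | s = 1.5 | s = 2.0 |
|---|---|---|---|
| 1 | 11% | 20% | 26% |
| 2 | 3.5% | 10% | 16% |
| 3 | 1% | 5% | 10% |
| 5 | <0.1% | 0.9% | 3% |
| 7 | <0.1% | <0.1% | 0.3% |

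False worsening beyond the same limits occurs about as often, within half a percentage point. These are probabilities for the BASFI domain on a form with that many items. They are not probabilities that ASAS20 changes.

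**4. A constructed case.** All baseline items are 6. Follow-up items are 6, 6, 6, 6, 6, 5, 5, 5, 4, 3. The full score is 52/10 = 5.2, an improvement of 0.8 units (0.8/6 = 13%), so the domain is not improved. At this baseline the 20% limit is 1.2 units. Scored from subsets, the domain counts as improved in:
- 2 of 10 one-item subsets (20%)
- 12 of 45 two-item subsets (27%)
- 51 of 252 five-item subsets (20%)
- 0 of 120 seven-item subsets

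**Scale-up.** If a share f of visit assessments has a BASFI from very few items, the observed ASAS20 rate at that visit cannot move by more than f, whatever the item SD. The documents do not give f. As an illustration, f = 1% caps the effect at 1 percentage point. The actual shift would be smaller, because most such forms fall outside the four deciding states or are classified correctly.

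**The case against.** A reader might infer several stronger points. The documents do not support them.

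- **That the SAP overrides the protocol's ten-item definition.** It does not. The SAP restates that definition and adds a rule where the protocol is silent. Protocol 9.4.3 also says efficacy data are presented using all available data.
- **That the SAP has a general two-thirds floor which BASFI escapes.** BASDAI total (4 of 6, 67%) and BASMI (all 5) do have floors, but neither is a main ASAS domain. The BASDAI-derived domain that enters ASAS20, morning stiffness, is accepted from one of two questions. A 7-of-10 floor (70%) is therefore a judgement and not an existing SAP convention.
- **That up to a quarter of responses could be wrong.** The 26% applies to one-item forms, at the top of the assumed SD range, and to the domain only.
- **That multiple imputation would recover scores set to missing.** It covers one treatment group, with stated visits up to Week 156, while the primary variable runs to Week 260.

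Two further objections have weight. The publications cited for the rule may contain a limit; they cannot be checked here, and no limit is carried into the SAP text. Protocol 8.1-8.3 provides source verification of primary-variable data and completeness review, which makes near-empty forms likelier to be noticed, although it sets no floor and cannot restore unanswered items. The study is also descriptive, with no formal hypotheses.

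What stands is that the written rule, applied literally, accepts a one-item BASFI as observed data in the primary variable.

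**Conclusion.** The point holds as a low-severity weakness in SAP 12.1, worth considering. Near-empty forms are scored unreliably: about 11-26% false domain improvement with one item, against under 0.5% with seven. This assumes an item SD of 1 to 2 units, items missing at random and no true change. Selective omission of particular tasks could add a systematic shift that these figures leave out. The effect on reported ASAS20 and ASAS40 rates is limited to the unstated, probably small, share of partly completed forms, and to those among them where BASFI decides the response. No test or decision threshold depends on it, but the response rates and their confidence intervals are the study's main efficacy output.

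**What to change.** In SAP 12.1, replace the missing-item sentence with: *BASFI is the mean of the non-missing items if at least 7 of the 10 are answered; otherwise BASFI is missing.* Add that a BASFI missing for this reason is handled in ASAS20/40 like any other missing main domain. State that handling explicitly if it is not already written down, including the case where the other three domains have all improved. The value is then missing in the observed-data tables and is imputed only where the SAP's multiple imputation applies (the 10 mg/kg - 150 mg group, visits as stated in 19.2.4). A count of BASFI scores based on fewer than ten items would show whether the issue matters in practice.

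The cost is a sentence or two and one line of derivation code. The downside is that a few BASFI values, and some ASAS evaluations, become missing. For ASAS40, whose remaining domain may not worsen at all, a floor makes spurious worsening smaller but cannot remove it.
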